3.4.2 Secondary Outcomes

The secondary outcomes are:

- *Children's Depression Rating Scale-Revised (CDRS-R):*

- *Variable type:* Continuous
- *Range and polarity:* This 17-item researcher administered interview has 3 items scoring between 1-5 and 14 items between 1-7. The total score ranges between 17-113. A higher score suggests greater levels of depressive symptoms, with a score of 40 indicating diagnosable depression.
- *Follow-up:* The CDRS-R is collected at baseline, 6 months post-randomisation and 12-months post-randomisation.
- *Behavioural Activation for Depression Scale (BADS-SF):*
 - *Variable type:* Continuous
 - *Range and polarity:* Each item is scaled from 0-6, giving a total score ranging between 0-54. A higher score represents increased behavioural activation.
 - *Follow-up:* The BADS-SF is collected at baseline, 6 months post-randomisation and 12-months post-randomisation.

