5.2.3 CDRS-R

The CDRS-R has 3 sub-scales containing 17 items overall. Items 4, 5 and 16 are scored from 1-5 and the remaining items are scored from 1-7. The raw scores for each sub-scale will be calculated and then an overall score will be calculated.

The overall raw scores will range from 17 to 113. These overall raw scores will be converted to corresponding T-scores as displayed on the questionnaire. The lower the T-score the less

likely for a depressive disorder diagnosis is to be made. The CDRS T-scores will be grouped into three categories, using a cut-off score of 54 and 64, such that a T-score of ≤ 54 is interpreted such that a depressive disorder is unlikely to be confirmed in any further evaluation, score of 55-64 suggests depression is possible to be diagnosed after further comprehensive testing (emerging depression) and scores >65 indicate likely depression.

Items 15 and 17 require the researcher to rate the child's facial expressions and body movement during the follow-up. The appointment may be via telephone or online (with no camera) which in these situations, the researcher would be unable to score these items. Only questionnaires with all items completed will be included in the secondary analysis model, however these participants will be included in a sensitivity analysis detailed in section 5.9.2.1.

Further information of the interpretation of the T-score for the CDRS-R can be found in the Appendix (section 8.2.2).

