5.8.2 Impact of Missing Data on the Primary Analysis

5.8.2.1 Missing covariates

To calculate the primary outcome measure of the RCADS T-scores, it requires the participants sex and age. As we are collecting gender, participants that select the options of 'non-binary' or 'prefer not to say' will be considered as missing and thus not be included in the primary analysis. We do not expect any missing data regarding the age of the participant as this is used to determine eligibility.

The impact of this on the primary analysis will be assessed using multiple imputation by chained equations. The imputation model will include key baseline variables (age, gender, baseline RCADS-25 T-score, baseline CDRS-R score, and baseline BADS-SF score). A 'burn –in' of 150 will be used and 50 imputed datasets will be created. The primary analysis will then be rerun within the imputed datasets and Rubin's rules will be used to combine the multiply imputed estimates.

In addition to the above analysis, patterns of missingness of covariates amongst participants will be summarised descriptively.

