5.9.2 CDRS-R

The CDRS-R will be analysed first using the T-scores as a continuous measure and second as an ordered categorical measure.

The continuous CDRS-R T-scores will be used as the response variable. This analysis will compare the adjusted mean difference of the CDRS-R score between treatment arms at both 6- and 12-months post randomisation. A linear mixed effects regression model will be used, replacing the baseline value of RCADS-25 T-Score to that of the baseline CDRS-R T-score, with all other fixed and random covariates remaining the same as the primary model.

For the second analysis, the CDRS-R T-scores will be categorised into three groups as defined in section 5.2.3. This analysis will compare the odds of being in a higher category than the non-diagnosable depression category for each treatment arm. A mixed ordinal logistic regression model will be used, replacing the baseline value of RCADS-25 T-Score to that of the baseline CDRS-R T-score, with all other fixed and random covariates remaining the same as the primary model. This will be analysed at both 6- and 12-months post randomisation. The proportional odds assumption for ordinal regression models will be assessed using the Brant test.

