Depressed Facial Affect	1 2 3 4 5 6 7	1 2 3 4 5 6 7	1 2 3 4 5 6 7	1 2 3 4 5 6 7	1 2 3 4 5 6 7	1 2 3 4 5 6 7	1 2 3 4 5 6 7	1 2 3 4 5 6 7	1 2 3 4 5 6 7	1 2 3 4 5 6 7	1 2 3 4 5 6 7	1 2 3 4 5 6 7																																																																																																																																																																																																																																	
Listless Speech	1 2 3 4 5	1 2 3 4 5	1 2 3 4 5	1 2 3 4 5	1 2 3 4 5	1 2 3 4 5	1 2 3 4 5	1 2 3 4 5	1 2 3 4 5	1 2 3 4 5	1 2 3 4 5	1 2 3 4 5	1 2 3 4 5																																																																																																																																																																																																																																
Hypoactivity	1 2 3 4 5 6 7	1 2 3 4 5 6 7	1 2 3 4 5 6 7	1 2 3 4 5 6 7	1 2 3 4 5 6 7	1 2 3 4 5 6 7	1 2 3 4 5 6 7	1 2 3 4 5 6 7	1 2 3 4 5 6 7	1 2 3 4 5 6 7	1 2 3 4 5 6 7	1 2 3 4 5 6 7	1 2 3 4 5 6 7																																																																																																																																																																																																																																

 
 = No apparent difficulties	= Clinically significant difficulties	= Severe clinically significant difficulties	
 
														= No apparent difficulties	= Clinically significant difficulties	= Severe clinically significant difficulties																																																																																																																																																																																																																													
= No apparent difficulties	= Clinically significant difficulties	= Severe clinically significant difficulties																																																																																																																																																																																																																																											

ParticipantID_p7
ID /

Instructions:

Rate each symptom area for this child by writing only one number in the box.
Write *NR* ("Not Rated") in the box if there is insufficient information to derive a rating.

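### An incomplete baseline CDRS-R interview leaves no baseline covariate, so the main CDRS-R models drop that participant's fully rated follow-ups; the cost is some precision in a secondary outcome, not bias

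*SAP*

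**What the plan says.** - **Time points (SAP 3.4.2).** "The CDRS-R is collected at baseline, 6 months post-randomisation and 12-months post-randomisation".
- **Scoring (5.2.3).** The 17 items are summed. "These overall raw scores will be converted to corresponding T-scores as displayed on the questionnaire". Unlike the RCADS-25 (5.2.1), PHQ-9A (5.2.2) and BADS-SF (5.2.4), the CDRS-R has no rule for replacing missing items.
- **Completeness (5.2.3).** "Only questionnaires with all items completed will be included in the secondary analysis model". The sentence continues: "however these participants will be included in a sensitivity analysis detailed in section 5.9.2.1". The paragraph opens with the reason: "Items 15 and 17 require the researcher to rate the child's facial expressions and body movement during the follow-up".
- **Unrated items on the form (8.2.2).** For any symptom area the rater may write NR "in the box if there is insufficient information to derive a rating".
- **Models (5.9.2).** The linear and the ordinal model each keep the primary model's terms, "replacing the baseline value of RCADS-25 T-Score to that of the baseline CDRS-R T-score".
- **Sensitivity analysis (5.9.2.1).** The 5.9.2 models are rerun with participants whose items 15 or 17 could not be rated because the appointment was by telephone or had no camera.
- **Missing covariates (5.8.2.1).** The section starts from sex and age: "To calculate the primary outcome measure of the RCADS T-scores, it requires the participants sex and age". Its imputation model includes the baseline RCADS-25, CDRS-R and BADS-SF scores, but only the primary analysis is rerun in the imputed data.
- **BADS-SF (5.2.4 and 5.9.3).** One missing item is mean-imputed. With more than one missing there is no score, and the BADS-SF model adjusts for the baseline score.

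**The concern.** A rule about which CDRS-R interviews can be scored as outcomes also decides, without saying so, who has a baseline covariate. A participant whose baseline interview has one unrated item has no baseline T-score. A mixed model that adjusts for that score cannot use any of the participant's rows, however complete the later interviews are.

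Section 5.1.1 commits the analyses to intention-to-treat unless stated otherwise. Here randomised participants with observed outcomes would leave because of a measurement taken before randomisation, and nothing in the plan states or justifies that. At stake are precision in the CDRS-R and BADS-SF comparisons and a handling choice that could be made after the data are seen.

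**Working it through.** **1. The plan's own figure.** Section 3.5 gives 86 per group for 90% power at d = 0.5, a design effect of 1.04 and 23% loss. A two-sample t-test with 86 per group has power 0.903. Inflating: 172 × 1.04 = 178.9, and 178.9 / 0.77 = 232.3, so 233 (234 if rounded per arm), close to the planned 236. This target is for the RCADS. The SAP gives no figure for the CDRS-R or for incomplete baselines.

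**2. Does the deletion happen?** A small mixed model was fitted to 182 participants with two complete follow-ups each (364 rows). With the baseline covariate missing for 18 of them, 164 participants and 328 rows remained: 18 × 2 = 36 complete follow-up rows were lost.

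**3. Does another section bring them back?**
- 5.9 carries over the primary model's missing-at-random assumption. In a likelihood-based mixed model that deals with missing outcomes; it does not fill a covariate.
- 5.8.2.1 does not rerun the CDRS-R or BADS-SF models.
- 5.9.2.1 covers only items 15 and 17 at non-visual appointments, gives no scoring rule and leaves the main models unchanged. Any other unrated item has no route back.

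**4. How many?** Expected at follow-up: 236 × 0.77 = 181.7. The share q of incomplete baselines is an assumption.

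| q | lost = 181.7 × q | power at d = 0.5, DE 1.04 |
|---|---|---|
| 0 | 0 | 0.91 |
| 5% | 9.1 | 0.89 |
| 10% | 18.2 | 0.88 |
| 20% | 36.3 | 0.84 |

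The power column is illustrative. It applies the RCADS effect size to the CDRS-R and uses an unadjusted t-test.

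**5. How much precision?** Simulation of 4,000 trials per setting: n = 182, one follow-up, baseline-outcome correlation 0.5, arm effect -0.5, baseline more often missing in severe cases. The table shows the standard deviation of the arm estimate.

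| q | deletion | mean fill + indicator | ratio |
|---|---|---|---|
| 5% | 0.1304 | 0.1285 | 1.015 |
| 10% | 0.1349 | 0.1306 | 1.033 |
| 20% | 0.1450 | 0.1321 | 1.098 |

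Two repeat simulations gave increases of 2.0%, 3.2% and 9.3%, and of 1.5%, 3.3% and 9.2%. The mean estimate was about -0.50 under both methods.

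**6. Hand check.** With outcome variance 1 and correlation 0.5, the residual variance is 1 - 0.25 = 0.75 where the baseline is known and about 1 where it is filled. The ratio of standard errors is then about √{0.75 / [(1 - q)(0.75 + 0.25q)]}:
- q = 5%: √[0.75 / (0.95 × 0.7625)] = 1.018
- q = 10%: √[0.75 / (0.90 × 0.775)] = 1.037
- q = 20%: √[0.75 / (0.80 × 0.80)] = 1.083

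This ignores the link between missingness and severity, and agrees with the simulation to about 1.5 percentage points.

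**The case against.** Several points on the other side stand in part.

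- **The rule may be meant for follow-up only.** The paragraph in 5.2.3 is about ratings made at follow-up appointments. A reader might infer that the SAP expressly applies the all-items rule to baseline, or orders deletion. It does neither: the rule names no time point, and deletion is what the software does by default. But on the narrower reading the plan still has no way to score an incomplete baseline, so the gap remains.
- **Section 5.9.2.1 offers a route back.** It does, for the one cause of unrated items that the SAP describes, and it is not tied to a time point. It remains a sensitivity analysis with no scoring rule.
- **Incomplete baselines may be rare.** Randomisation follows a completed baseline visit (3.6), and missing data on returned forms are pursued with the research assistants (4.3). The NR option shows that an unrated item is possible, not that it is common.
- **The RCADS-25.** A reader might carry the point over to the primary analysis. There it is minor. Up to three anxiety and two depression items are imputed (5.2.1), and the imputation model in 5.8.2.1 includes the baseline score. Where the T-score is missing because of sex, the follow-up T-scores are missing too, so filling the baseline recovers nobody.
- **The ordinal model.** Odds ratios are non-collapsible, so filling mixes adjusted and unadjusted effects. A large-sample check (log-odds effect -0.9, baseline missing at random) put the filled estimate about 1-3% nearer zero than the complete-baseline one at 5-10% missing, and 4-8% nearer at 20%. This stands and shapes the fix.

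**Conclusion.** The point holds as a minor one. In the main CDRS-R models, and in the BADS-SF model when more than one baseline item is missing, an unscorable baseline removes observed follow-ups for no good reason.

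The effect is lost precision in secondary outcomes. At assumed rates of 5%, 10% and 20%, about 9, 18 and 36 of some 182 followed participants are lost, and the standard error is about 1.5%, 3% and 9% larger. These figures rest on a baseline-outcome correlation of 0.5, the planned 23% loss to follow-up, and rates of incompleteness that the SAP does not give.

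Two stronger readings are not supported. One is that the arm comparison is biased. The baseline precedes randomisation, so whether an item is rated cannot depend on allocation, and the linear simulations showed no bias either way. The other is to apply the rates to all 236 randomised, giving about 12, 24 or 47. That counts people who are expected to have no follow-up to lose. The sample size is not affected.

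**What to change.** - In 5.2.3, state that the all-items rule applies to the follow-up outcome only.
- In the linear CDRS-R and BADS-SF models, replace a missing baseline score with the mean of the observed baselines pooled over both arms, add a missing-baseline indicator, and keep all observed follow-ups.
- In the ordinal CDRS-R model, use the same fill and report the complete-baseline result beside it.

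This takes a sentence or two in the SAP and a line of code per model. The downside is one extra parameter in each model where any baseline is missing, and one additional reported result for the ordinal model.

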5.2.4 BADS-SF

The BADS-SF consists of 9 items that are scored from 0-6 and split across two sub-scales. For each item the greater the score suggests higher behavioural activation except for items 1, 6, 7 and 8 whereby the scoring is reversed. The total score ranges from 0-54 with the reversed scores considered e.g., a score of 0 would be included in the calculation as a 6, 1 as a 5 and so on.

There is no guidance for the BADS-SF regarding scoring questionnaires with missing items. Here we use the rule where the missing items of a Patient Reported Outcome Measure (PROM) should only be replaced with the means of the non-missing items to facilitate the calculation of a score, if the number of non-missing items is less than 10% of the total number of items in the PROM. In this case, mean imputation will be used if one item is missing in the BADS-SF and unable to be scored if more than one item is missing.

5.2.5 Aspects of care

The aspects of care questionnaire consist of 8 items, collected at 6- and 12-month follow-up points, that will be used to evaluate the level of compliance to the intervention and any contamination observed in the usual care group. Each item has discrete checkbox options of "Yes", "No" and "I don't know", with an answer of "Yes" suggesting that the young person did complete the activity specified. Items 2, 4, 6, and 8 are of particular interest as a positive answer to these items suggests that the young person had been involved in BA related activities during their time in the study.

5.3 Derivation of Variables and Outcomes

5.3.1 RCADS T-scores

The RCADS T-scores are derived by transforming the raw scores depending on sex and the grade they are in at school. As UK schools do not use grades, the young person's age will be used to approximate their school grade. This will be approximated by adding 6 to the young person's age as suggested by the RCADS-25 Child Version Scoring Resources (Ebesutani et al (2012)). Table 2 shows the specific transformations for each permutation of sex and age.

Table 2: RCADS raw score transformations to derive T-scores for each sub-scale and overall.

Sex	Age (Grade)	Depression T-score	Anxiety T-score	Overall T-score
Male	10 (4)	$((Score - 9.90)*10)/4.93 + 50$	$((Score - 15.19)*10)/7.09 + 50$	$((Score - 25.10)*10)/11.10 + 50$
	11-12 (5-6)	$((Score - 7.13) *10)/4.22 + 50$	$((Score - 11.63)*10)/6.45 + 50$	$((Score - 18.76)*10)/9.38 + 50$
	13-14 (7-8)	$((Score - 7.56) *10)/3.75 + 50$	$((Score - 10.48)*10)/5.36 + 50$	$((Score - 18.04)*10)/7.92 + 50$
	15-16 (9-10)	$((Score - 7.50) *10)/4.18 + 50$	$((Score - 9.70)*10)/5.45 + 50$	$((Score - 17.20)*10)/8.53 + 50$
	17-18 (11-12)	$((Score - 7.64) *10)/4.37 + 50$	$((Score - 9.96)*10)/4.32 + 50$	$((Score - 17.60)*10)/7.24 + 50$
Female	10 (4)	$((Score - 9.68)*10)/4.97 + 50$	$((Score - 16.25)*10)/8.42 + 50$	$((Score - 25.93)*10)/12.24 + 50$
	11-12 (5-6)	$((Score - 8.03)*10)/5.00 + 50$	$((Score - 13.49)*10)/7.62 + 50$	$((Score - 21.53)*10)/11.73 + 50$
	13-14 (7-8)	$((Score - 8.08)*10)/4.34 + 50$	$((Score - 12.74)*10)/6.22 + 50$	$((Score - 20.82)*10)/9.46 + 50$
	15-16 (9-10)	$((Score - 8.14)*10)/4.37 + 50$	$((Score - 11.31)*10)/5.33 + 50$	$((Score - 19.45)*10)/8.63 + 50$
	17-18 (11-12)	$((Score - 8.59)*10)/3.67 + 50$	$((Score - 11.50)*10)/5.34 + 50$	$((Score - 20.09)*10)/7.79 + 50$

5.3.2 Other variables

- Age: Derived from the child's date of birth at the time of baseline completion.
- Sex: Derived from the recorded gender at baseline with Male and Female options assumed to be the child's sex at birth.
- Therapist: Each participant will be assigned to a single therapist. In the scenario that a participant has seen more than one therapist, the therapist that conducted the majority of the participants sessions will be used (this is assuming that more sessions will lead to a greater rapport between the young person and the therapist).

5.4 Trial Progression

The flow of participants from eligibility, randomisation, to follow-up and analysis of the trial will be presented in a CONSORT flow diagram (Figure 1). Withdrawal and reasons for withdrawal will be summarised descriptively by treatment group.

5.5 Demographic and Baseline Data

All participant demographic and baseline characteristics will be summarised descriptively by trial group, both for patients 'as randomised' and 'as analysed'. The 'as randomised' population will comprise all eligible participants who were randomised, while the 'as analysed' population will comprise all patients included in the primary analysis. No formal statistical comparisons of characteristics will be undertaken between groups. Continuous measures will be summarised using descriptive statistics (n, mean, standard deviation, median, IQR, minimum and maximum), while categorical data will be reported as counts and percentages.

5.6 Treatment Delivery

Data involving the delivery of BA and UC sessions will be summarised descriptively by treatment group and overall (Table 4). The following information will be summarised:

- Number of sessions attended (with percentage of sessions booked / available to attend).
- Length of time to prepare for the session.
- Time taken to complete the session.
- Length of time spent on administrative activities after the session.
- Location of the session i.e. Online, in person or by telephone.
- Number and percentage of BA participants that fully completed the full course suggesting full compliance with the intervention.
- Number and percentage of UC participants marked with possible contamination of BA.
- Aspects of care items individually summarised at 6- and 12-month time points.

No formal statistical comparisons of characteristics will be undertaken between groups.

5.7 Primary Analysis

The RCADS-25 will be summarised descriptively at each collected time point by trial arm. Mean scores and confidence intervals will be illustrated graphically.

The primary analysis will be conducted on an intention to treat (ITT) basis, including patients in the groups to which they were randomised.

The primary analysis will compare the continuous RCADS-25 T-score between treatment arms at 6-months post randomisation. This will be analysed using a mixed-effects linear regression model, including all available follow-up time points. The model will adjust for the RCADS-25 at baseline and include as fixed effects: trial arm, arm-by-time interaction, age, sex, setting and site. Random effects will be included to account for the repeated measures within patients and for possible clustering by therapist, patient, and therapist nested within treatment arm.

Adjusted mean differences between treatment groups will be presented at each timepoint with an associated 95% confidence interval (CI) and p-value.

For the modelling of repeated measurements, the best fitting (based on Akaike information criteria (AIC) and Bayesian information criteria (BIC)) covariance pattern that is not significantly different from an unstructured pattern will be selected. The model will provide an overall treatment effect over 6 months as well as estimates at the 12-month time point. These will be reported as mean differences between treatment groups with 95% confidence intervals and associated p-values. The estimate at the 6-month time point will serve as the primary endpoint.

Data will be assumed missing at random. The assumptions of normality and homoscedasticity of residuals will be checked using graphical methods, and if the assumptions are in doubt the data will be transformed prior to analysis or alternative non-parametric analysis methods will be explored.

The primary analysis will be checked by a second statistician before the release of any results.

5.8 Secondary Analyses

The following sections detail any secondary analyses that will be performed on the primary outcome. For example, any sensitivity analyses to determine if results of the primary analysis change under different conditions.

5.8.1 Complier-Average-Causal-Effect (CACE) Analysis

Complier Average Causal Effect (CACE) analysis will be carried out for the RCADS-25 at the 6- month time point. Compliers are defined as participants who received their allocated treatment.

The CACE analysis will be implemented using an instrumental variable regression model with treatment allocation as the instrument and received treatment as the exogenous variable. The model will control for the following variables used in the primary analysis; treatment arm, age, and sex. Separate CACE analyses will be carried out for the following definitions of compliance:

- 1) Minimal compliance: for a participant to be classed as having met the conditions for minimal compliance to the intervention, they should have completed at least 5 sessions (this is the approximate number of sessions required to cover modules 1-3 of the BA intervention)
- 2) Full compliance: for a participant to be classed as having met the conditions for full compliance, they must have completed at least 8 sessions (this is the approximate number of sessions required to cover all components of the BA intervention).

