3.3 Interventions

3.3.1 Behavioural activation

A bespoke, standardised BA package was developed which was inspired and informed by published literature, public and patient involvement (PPI) activities and a feasibility study.

The BA sessions with a professional will guide and support each young person to identify, schedule, complete and monitor pleasures, necessities and goals in day-to-day life that connect with what and who is important to them. These may be things that the young person has stopped doing or doing less, which they can start doing again or more. There may be things that the young person would like to do or things that the young person never thought of doing for which they need help to start. There may be things that they have been doing routinely but no longer enjoy and need to change them in some way.

The young person will keep a diary in which they will make a note of each activity that they complete. Some of these activities will be scheduled and others will be unplanned, routine or spontaneous. The young person will score enjoyment, achievement and/or connection for each activity on a 0-10 scale (0=no enjoyment/achievement/connection, 10=great enjoyment/achievement/connection). Over the course of the week, activities that score high

on enjoyment, achievement and connection are highlighted and encouraged. Activities that score low can be reduced or changed so that they become more enjoyable or rewarding.

Activities that have not been completed can be postponed, cancelled, or changed – depending on the reasons for not being completed (the young person did not consider them important, or they were too difficult or other activities took priority). A graded and stepped approach to activities will help young people overcome obstacles such as hesitation and tiredness that are to be expected with depression. Some activities may actually make young people feel worse or may be harmful, destructive or counterproductive; these need to be identified and reduced/stopped.

The BA programme is organised in 5 “modules” which can be completed in up to 8 weekly sessions of 30-40 minutes each in a blended model of professional-guided sessions and self-directed activities. A 5-module approach has been used by McCauley et al (2016a) in their published guide (pp. 12-13). The content of these 5 modules is bespoke to ComBAT.

Table 1: The Five BA modules in ComBAT.

Module	Topics covered

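### The CACE model in SAP 5.8.1 uses randomised allocation both as the instrument and as a control, so it is not identified as written; it also calls received treatment exogenous and leaves out the baseline score

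*SAP*

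**What the plan says.** SAP 5.8.1 specifies a CACE analysis of the RCADS-25 at 6 months using an "instrumental variable regression model with treatment allocation as the instrument and received treatment as the exogenous variable". The next sentence gives the covariates: "The model will control for the following variables used in the primary analysis; treatment arm, age, and sex".

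The primary model in SAP 5.7 is adjusted more fully: "The model will adjust for the RCADS-25 at baseline and include as fixed effects: trial arm, arm-by-time interaction, age, sex, setting and site". Baseline RCADS-25, setting and site are not carried into the CACE list.

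Two definitions of compliance are analysed separately. For minimal compliance, "they should have completed at least 5 sessions (this is the approximate number of sessions required to cover modules 1-3 of the BA intervention". The stricter definition, full compliance, reads: "they must have completed at least 8 sessions (this is the approximate number of sessions required to cover all components of the BA intervention". Section 3.3.1 describes the BA programme as five modules "which can be completed in up to 8 weekly sessions of 30-40 minutes each". Section 5.6, on treatment delivery, reports the number of BA participants who finished the whole course and takes that as indicating full compliance.

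**The concern.** An instrument works only if it is kept out of the outcome equation. Here allocation is the sole instrument, and the same variable is then put into the outcome equation as treatment arm. Once arm is a control, allocation carries no further information about who received treatment, and the model has no solution for the effect of interest.

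The label on received treatment adds to the difficulty. Attendance is chosen after randomisation and may depend on prognosis, which is why an instrument is needed. If received treatment were exogenous, no instrument would be required. Taken together, the two sentences give allocation two incompatible roles and received treatment the wrong one. The analyst must depart from the text to fit anything, and a repair made after the data are seen weakens prespecification.

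Two lesser matters sit in the same section. Leaving out the baseline score gives up precision that is available from data already collected. And the full-compliance threshold equals the upper limit given for the programme, so someone who covers all five modules in fewer sessions counts as a full complier under 5.6 but as untreated under 5.8.1.

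**Working it through.** SAP 5.8.1 states no numerical result to reproduce. The checks are on its model.

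**1. Identification (no assumed figures needed).**
- Outcome equation as written: received treatment, constant, arm, age, sex = 5 parameters.
- Instrument set as written: allocation, plus the included controls (constant, arm, age, sex). Allocation duplicates arm, so these 5 columns have rank 4.
- Identification requires the cross-product of instruments and regressors to have rank 5. It has rank 4, so the condition fails.
- Equivalently, the variance of allocation left after regressing it on the controls is 0 (numerically about 3e-31).
- With arm removed: received treatment, constant, age, sex = 4 parameters; rank 4. The residual variance of allocation given the controls is 0.246, and the model is just identified.

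**2. Cost of omitting the baseline score.** With correlation r between the baseline and 6-month scores, adding baseline multiplies the residual SD by sqrt(1 - r^2), so omitting it enlarges the SE by 1/sqrt(1 - r^2). The SAP gives no r; three values are assumed.
- r = 0.3: 1/sqrt(0.91) = 1.05, about 5% larger.
- r = 0.5: 1/sqrt(0.75) = 1.15, about 15% larger.
- r = 0.7: 1/sqrt(0.51) = 1.40, about 40% larger.

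A two-stage least squares simulation agrees. It used 2,000 replicates per setting, N = 182 from 236 x 0.77 = 181.7, and an assumed 60% complier share. The mean SE was about 0.25 SD without baseline, and 0.24, 0.22 and 0.18 SD with it, for r = 0.3, 0.5 and 0.7. At a true effect of -0.5 SD, mean estimates at that share were -0.48 to -0.50 both with and without baseline, so the loss is of precision only.

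**3. Full-compliance threshold (illustration only).** Ignoring covariates, the estimator is the ITT effect divided by the share classed as compliers. Assume that 70% of the BA arm reach 5 sessions, that each of them gains 0.5 SD, and that nobody below 5 gains anything.
- ITT = 0.70 x 0.5 = 0.35 SD.
- 5-session CACE = 0.35 / 0.70 = 0.50 SD, the assumed truth.
- 8-session CACE = 0.35 / 0.50 = 0.70 SD if 50% reach 8.
- 8-session CACE = 0.35 / 0.30 = 1.17 SD if 30% reach 8.
- If all 70% reach 8, it is 0.35 / 0.70 = 0.50 SD, with no inflation.
- If those with 5 to 7 sessions gain nothing, the ITT is 0.5 times the share reaching 8, and the 8-session CACE is again 0.50 SD.

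The direction is therefore upward whenever participants below 8 sessions benefit. The size depends on attendance and dose-response, which the SAP does not give.

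**The case against.** The strongest reply is that this is a drafting slip. The same three covariates are listed for the pattern-mixture regression in SAP 5.8.2.2, where treatment arm does belong. Section 5.8.1 names the method and the instrument, so a statistician can see what was meant, and the literal model fails visibly rather than giving a wrong answer unnoticed. This is a fair account of how the error may have arisen, and it limits the harm. It does not make the text usable: the written specification cannot be fitted, and any repair would have to go on the Analysis Plan Departure Log under SAP 2.3.2.

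On the baseline score, the reply is that under randomisation its omission is a matter of efficiency. That stands. A reader might infer that the CACE is biased without it; neither the theory nor the simulation supports that. Adding setting and site is a matter of preference and is not argued here.

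On the threshold, a reader might see a flat contradiction between sections 3.3.1 and 5.8.1, or expect a grossly inflated full-compliance effect. The document supports neither. Someone who attends 8 sessions satisfies both passages, and 5.8.1 calls its figure approximate. The session record in 3.4.3 also distinguishes assessment, intervention and review sessions, so the count in 5.8.1 need not be a count of module sessions. Treating people below a cut-off as untreated is common to any binary CACE. The prespecified 5-session analysis counts those who finish in 5 to 7 sessions as compliers, so it partly covers the problem. A further CACE with session count as a continuous exposure could be considered, but it brings its own linearity assumption, and its absence is not a fault.

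**Conclusion.** The point holds on the model specification. As written, the CACE model is not identified; this is algebra and rests on no assumed number. Calling received treatment exogenous is wrong in the same passage. Omitting the baseline score costs about 5% to 40% in standard error over assumed correlations of 0.3 to 0.7, without bias.

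The meaning of full compliance is a tension to be reconciled, not a proven error. The illustrative 0.70 and 1.17 SD, against an assumed 0.50 SD, show the direction of a possible distortion and are not a forecast for this trial.

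A reader might also infer that the trial's main conclusion is at risk. It is not: the CACE is a secondary analysis of the primary outcome. The intention-to-treat comparison in SAP 5.7 and the sample size in SAP 3.5 do not depend on it.

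**What to change.** In SAP 5.8.1:

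1. Delete treatment arm from the list of controls, so that allocation enters only as the excluded instrument.
2. Describe received treatment as the endogenous variable.
3. Add the baseline RCADS-25 T-score to the controls alongside age and sex.
4. Reconcile sections 3.3.1, 5.6 and 5.8.1 on what counts as full compliance, and state which session types are counted. No session number is proposed here; that is for the trial team. When the two CACE results are reported, note that the full-compliance estimate assumes no effect of allocation in participants below its threshold.

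The cost is a few words in the SAP and a few lines of code, with no new data. It should be done before outcome data are analysed by arm, so that it is an amendment to the plan and not a logged departure.
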